1.2 Pegsitacianine Clinical Trial Background

Three clinical studies have been performed using pegsitacianine. The study *ON-1001: Image-Guided Surgery for Tumor Detection in Solid Tumors Using the pH Activated Micellar Probe ONM-100: The SHINE Study*, was conducted in the Netherlands at the University Medical Center Groningen and completed in 2019.¹⁹ The completed Phase 2 study, *ON-1002: A Study to Evaluate ONM-100, an Intraoperative Fluorescent Imaging Agent for the Detection of Cancer* ([NCT03735680](https://clinicaltrials.gov/ct2/show/NCT03735680)) was a multicenter trial in the United States. *ON-1004* was a Phase 1 normal healthy volunteer study to further evaluate the pharmacokinetic profile of pegsitacianine.

The purpose of the ON-1001 study was to investigate the safety, pharmacokinetics and feasibility of pegsitacianine as an intraoperative optical tracer for the detection of tumors and metastatic lymph nodes in solid cancers. Additionally, the study investigated the optimal dose range of pegsitacianine for an adequate tumor-to-background/contrast-to-noise ratio of fluorescence obtained intraoperatively and with *ex vivo* specimens using indocyanine green (ICG) compatible cameras and imaging devices. A single pegsitacianine micelle dose was administered intravenously (IV) as a one to five-minute infusion to patients in five dose cohorts (0.1, 0.3, 0.5, 0.8, and 1.2 mg/kg) with three patients per cohort in Phase 1A, and 15 patients at a dose of 1.2 mg/kg in Phase 1B. Near-infrared (NIR) imaging was conducted intraoperatively, on the back table, and postoperatively of the primary tumor, lymph nodes, and pegsitacianine guided biopsies. Additionally, the bread loaf slices from the primary tumor were also imaged postoperatively. The median tumor-to-background (TBR) value from all bread loaf slice image analysis (n = 97 slices from 27 patients) was determined to be 4.5 with an interquartile range of 3.1. Additionally, pegsitacianine demonstrated a sensitivity of 100% across all tumor types tested with a specificity of 75% and 57% in breast cancer and head and neck squamous cell carcinoma (HNSCC), respectively.¹⁹

The purpose of the ON-1002 study was to investigate whether pegsitacianine can be used to image primary tumors and metastatic lymph nodes using an imaging schedule earlier than 24 ± 8 hours postdose in patients undergoing routine surgery of their solid cancers and whether the diagnostic performance to detect metastatic lymph nodes can be improved by optimizing the dose and the imaging schedule. The study was designed to be executed in three parts:

Part 1 was designed to evaluate the dose(s) at which pegsitacianine fluorescence imaging is feasible at 3 ± 2 hours postdose and, if needed, at an alternate postdose imaging schedule, for the

detection of metastatic lymph nodes and primary tumors after a single IV dose of pegsitacianine in patients with HNSCC or breast cancer undergoing routine surgery. Part 1 also evaluated safety at the dose(s) used to assess imaging feasibility and to select the dose(s) and postdose imaging schedule(s) that are safe and provide optimal imaging of solid tumors and metastatic lymph nodes; the dose and time postdose chosen for the detection of primary tumors and metastatic lymph nodes may be the same or different.

[figure not shown]
Part 2 of the ON-1002 study was designed to verify the safety and diagnostic performance of pegsitacianine compared to standard pathology at the dose(s) and postdose imaging schedule(s) selected from Part 1 for the detection of the primary tumors and the metastatic lymph nodes in a variety of solid cancers (which may include HNSCC, breast cancer, colorectal cancer, urothelial cancer, prostate cancer, ovarian cancer and/or non-small-cell lung carcinoma [NSCLC]). In addition, the PK profile of pegsitacianine at the dose(s) and postdose imaging schedule(s) used to assess optimal imaging in Part 1 and Part 2 was assessed.

Part 3 was used to assess the safety and efficacy (sensitivity and positive predictive value [PPV]) of pegsitacianine at a dose of [REDACTED] mg/kg for intraoperative imaging during HNSCC surgery, administered at [REDACTED] hours prior to surgery, in addition to a set of secondary and exploratory endpoints to further assess performance.

ON-1004 was a Phase 1 study conducted in normal, healthy volunteers. The study is designed to comprehensively evaluate the pharmacokinetic profile of pegsitacianine.

[figure not shown]
1.3 Pharmacodynamics and Dose Selection

The pharmacodynamic profile, and its relation to dose schedule selection of pegsitacianine was evaluated *in vivo* and *ex vivo* using intraoperative near-infrared cameras in both the ON-1001 and ON-1002 studies. The mean fluorescence intensities and tumor-to-background (TBR) ratios for subjects receiving [REDACTED] were not significantly different across the two studies to date. (The red line represents the average TBR calculated across all patients in each study).

All dose levels investigated in the ON-1001 Phase 1 Trial were imaged 24±8 hours following the completion of the pegsitacianine infusion

[figure not shown]
Phase 2: In Vivo Tumor-to-Background Ratios

The ON-1002 Phase 2 Trial investigated a range of dose schedules across the patient population as depicted in the above figure

Calculated TBR ratios across all evaluable subjects from both clinical studies show the absence of a dose-schedule to TBR relationship. However, evaluation of mean fluorescence intensity

(MFI) values of the tumor areas from the ON-1001 study do demonstrate a dose-dependent increases in MFI.

MFI values of tumor and normal tissue present on bread loaf slices as determined by pathology

Given the enhanced fluorescence of tumor areas at the higher doses of pegsitacianine, a dose of mg/kg was chosen as the ideal dose for the continued evaluation of pegsitacianine in the completed ON-1002 study, as well as the proposed ON-1003 clinical trial.

2. STUDY OBJECTIVES

2.1 Primary Objective

The primary objective of this study is to determine if administration of pegasitacianine (mg/kg) results in the detection of metastatic disease left behind following standard of care surgical resection of peritoneal metastases.

2.2 Secondary Objectives

Key secondary objectives are to demonstrate an acceptable safety profile, reliable sensitivity, specificity, negative predictive values, and positive predictive values of the imaging agent at the level of the individual specimens

2.3 Exploratory Objectives

Assess the how the normalized SBR value affects the diagnostic accuracy of pegasitacianine in detection of metastatic disease vs. normal tissue.

3. STUDY PLAN

3.1 Overall Design

This Phase 2 study will be a an interventional, open-label, single arm trial where each patient is his/her own “intrapatient” control usin two Grou s. All patients will receive a single mg/kg dose of pegasitacianine prior to standard of care surgery.

Patients enrolled in Group 1 of the study will have a biopsy confirmed diagnosis of non-mucinous peritoneal carcinomatosis, defined as less than, or equal to 50% mucin in the sample, with a suspected Peritoneal Carcinomatosis Index (PCI) greater than or equal to . Group 2 of the study will include patients with a suspected PCI greater than or equal to and a biopsy confirmed diagnosis of mucinous peritoneal carcinomatosis, defined as > 50% mucin in the sample. A total of approximately 60 patients will be enrolled across both Groups. Enrollment will be open first to Group 1 with the opportunity to open Group 2 for enrollment following the demonstration of satisfactory pegasitacianine sensitivity and specificity values of 70% or greater in Group 1.

In both Groups 1 and 2, the surgeon will perform their SOC resection of visible metastases and image each resected specimen, and normal specimens on an area of normal tissue using the intraoperative NIR camera; no investigative NIR imaging of the peritoneal cavity will be performed at this time. The SOC specimens are to be resected upon the initiation of surgery and imaged on a section of normal tissue (i.e., mesentery). Specimen names and fluorescence status will be dictated by the surgeon and documented in the Imaging Workbook by the Clinical Research Coordinator.

At the conclusion of SOC resection, the intraoperative NIR camera will be used to investigate the peritoneal cavity further for evidence of residual metastases highlighted by fluorescence using the approach that is performed for the calculation of the Peritoneal Carcinomatosis Index (i.e., 13 regions). Additional fluorescent specimens will also be imaged prior to excision and subsequently following resection on an area of normal tissue prior to sending all surgical specimens to pathology for examination. The fluorescence status of each specimen, as called out by the surgeon, will then be directly correlated to the histopathological outcomes of each specimen dictated in the final pathology report. This study design enables the calculation of pegsitacianine sensitivity, specificity, NPV, and PPV and the level of the specimens. Additionally, Completeness of Cytoreduction (CC) scores can be calculated following SOC resection and then adjusted following the additional resection of fluorescent metastases otherwise unknown to the surgeon. The schedule of events for this study is presented in Appendix 1.

3.2 Imaging Assessments

Imaging assessments will include the calculation of mean fluorescence intensity (MFI) of all collected surgical specimens. Specimens will be imaged both prior to excision (for post-SOC specimens) and immediately following on a piece of representative normal tissue (all specimens). MFI values will be used to further compute SBR values for the collected specimens. Correlation of imaging observations to pathological outcomes of each specimen will be used to understand pegsitacianine performance (i.e., PPV, NPV, Sensitivity, Specificity). Imaging assessments may be performed at the Group level to accommodate for any confounding data between the two Groups.

3.3 Safety Assessments

Safety assessments will include adverse events (AEs), clinical laboratory test results (hematology and serum chemistry), vital sign measurements (blood pressure, pulse, respiratory rate, and oral temperature), physical examination findings, and 12-lead electrocardiogram (ECG) results.

4. STUDY DRUG DOSAGE AND ADMINISTRATION

On Da 0 of the stud the atient will receive a mg/kg dose of pegsitacianine

The volume of drug and rate of infusion will vary by patient and be reliant on the overall required dose.

4.1 Prohibited Medications and Restrictions

Subjects may not take or receive the following:

- [REDACTED]
- Concomitant medication with a high probability of [REDACTED], as judged by the PI

Any concomitant medication deemed necessary for the welfare of the subject during the study may be given at the discretion of the investigator. However, it is the responsibility of the principal investigator to ensure that details regarding the medication are recorded in full in the subject's electronic case report form (eCRF). This record will include all prescription drugs, herbal products, vitamins, minerals, and over-the-counter medications. Any changes in concomitant medications also will be recorded in the subject's eCRF.

4.2 Study Drug Description

Pe_sitacianine is a novel micelle-based fluorescent ima in a ent. The micelles are comprised of a [REDACTED] conjugated to ICG, an FDA-approved fluorophore.

[figure not shown]
Pegsitacianine drug product is supplied as a greenish sterile frozen a ueous solution com osed of e sitacianine dru substance formulated as a [REDACTED] [REDACTED]. Each single-use vial contains 3 mL of pegsitacianine Injection for IV use. The product is limited to investigational use only.

[figure not shown]
All constituents of pegsitacianine are either used in an FDA approved drug, on an FDA list of constituents of food, or concluded to be safe for ingestion by an expert panel commissioned by the World Health Organization (WHO) (EAFUS, 2018; WHO, 1998).

4.3 Study Drug Safety

The most common and anticipated adverse events related to pegsitacianine include infusion related reactions. These reactions occur in about 1 in 3 patients and tend to be mild or moderate in severity. In general, these reactions initiate within 5 minutes of infusion start and resolve within minutes after onset.

Over the doses evaluated in the Phase 1 ON-1001 study (0.1-1.2 mg/kg), pegsitacianine was well tolerated in patients with solid tumors (HNSCC, BC, CRC, or EC) and showed no dose-limiting toxicity (DLT) (hence the maximum tolerated dose was not reached during the study) or study-drug-related serious adverse events (SAEs). Since no pegsitacianine-related SAEs were reported in Phase 1a, the highest dose from Phase 1a (1.2 mg/kg) was selected for further evaluation of safety, PK, and imaging feasibility of pegsitacianine in Phase 1b in 15 additional patients across 4 tumor types (BC, HNSCC, CRC, EC) at administration 24 (± 8) hours before surgery (and imaging).

Apart from 1 moderate (Grade 2) event of hypotension, there were no clinically significant findings with respect to vital signs.

No patient had a suspected unexpected serious adverse reaction (SUSAR), withdrew from the study due to a TEAE, or had an abnormal electrocardiogram (ECG) that was considered clinically meaningful.

In the completed Phase 2 study, a total of 30 patients have been administered pegsitacianine at doses of 1, 2, or 3 mg/kg with surgery occurring between 3 and 24 hours post-administration of drug. A total of 26 out of 30 subjects (87%) experienced at least one TEAE. In total, 88 TEAEs were documented across the 30 patients. 58 (66%) of the TEAEs were determined to be mild (Grade 1) and all but three TEAEs have resolved. The most commonly encountered TEAE was the sensation of feeling cold, either at the injection site or throughout the body, which was reported for 11 out of the 58 (19%) Grade 1 TEAEs; all TEAEs attributable to feeling cold were resolved.

4.4 Study Drug Packaging and Storage

Frozen vials of pegsitacianine are stored at [REDACTED]. Drug product vials are stable for up to 24 months (stability testing on ointment final formulation samples may be required and stored at [REDACTED]).

Prior to administration the frozen formulation is thawed at room temperature to a clear greenish-colored solution

All formulations at different stages of administration (frozen, during thawing, and upon preparation in a syringe) are to be protected from light.

4.5 Drug Accountability

The investigator will maintain accurate records of receipt of all study drug, including dates of receipt. In addition, accurate records will be kept regarding when and how much test article is dispensed and used by each subject in the study. Reasons for departure from the expected dispensing regimen must also be recorded. At the completion of the study, to satisfy regulatory requirements regarding drug accountability, all study medication will be reconciled and retained or destroyed according to applicable state and federal regulations.

5. SUBJECT ENROLLMENT

5.1 Inclusion Criteria

For inclusion in the study, each subject is required to meet all of the following criteria:

[figure not shown]
1. Adults 18 years of age and older
2. [REDACTED]

3. Suspected Peritoneal Carcinomatosis Index greater than or equal to [REDACTED]
4. Acceptable hematologic status, kidney function and liver function (as standard surgery protocol requires), as determined by the Investigator
5. Documented negative serum pregnancy for women of childbearing potential
6. Male patients and female patients of child-bearing potential (i.e. premenopausal women with intact reproductive organs and women <2 years after menopause) must agree to and comply with using medically acceptable contraception including surgical sterilization (e.g. hysterectomy, bilateral oophorectomy, bilateral tubal ligation), intrauterine device, oral contraceptive, contraceptive patch, long acting injectable contraceptive, partner's vasectomy, double-barrier method (condom or diaphragm plus spermicide or condom plus diaphragm), or abstinence during the trial and for 6 months thereafter
7. Agreement to abstain from heavy alcohol consumption (>4 drinks/day) 72 hours prior to administrations and for minimum of 10 days post-surgery
8. Agreement to complete all follow-up visits
9. Willing and able to provide written informed consent

5.2 Exclusion Criteria

Any of the following will be regarded as a criterion for exclusion of a subject from the study:

1. Known hypersensitivity or allergy to indocarbazine JCG [REDACTED]
2. Tumor locations the surgeon deems unfeasible to image intraoperatively
3. Excessive and/or generalized metastatic disease deemed inoperable by the surgeon [REDACTED] is deemed unlikely by the surgeon
4. Life expectancy less than 12 weeks
5. Karnofsky Performance Status less than 70%
6. Lab values that in the opinion of the investigator would prevent surgery
7. Medical or psychiatric conditions that would impair informed consent
8. Pregnant or lactating
9. Taking or plan to take medications with significant risk of hepatotoxicity
10. Any other significant medical condition the investigator deems inappropriate for the trial

5.3 Randomization Procedures

N/A

5.4 Blinding Procedures

Not applicable; this is an open label study.

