	
specimens on an area of normal tissue within the surgical field using the intraoperative NIR camera. The SOC specimens are to be resected upon the initiation of surgery and imaged on a section of normal tissue (i.e., mesentery). Specimen names and fluorescence status will be dictated by the surgeon and documented in the Imaging Workbook by the research coordinator.
 
At the conclusion of SOC resection, the intraoperative NIR camera will be used to investigate the peritoneal cavity further for evidence of residual metastases highlighted by fluorescence. Additional fluorescent specimens will be imaged in situ and then ex situ on an area of normal tissue within the surgical field prior to sending all surgical specimens to pathology for examination. The fluorescence status of each specimen will then be directly correlated to the histopathological outcomes of each specimen. This study design enables the calculation of pegasitacianine sensitivity, specificity, NPV, and PPV. Additionally, Completeness of Cytoreduction (CC) scores can be calculated following SOC resection and adjusted following the resection of additional fluorescent metastases, if warranted.

Endpoints	
Primary Endpoints:
 
 • Detection of disease left behind following SOC resection of peritoneal metastases. Detection of a single additional tumor-containing specimen excised as a result of pegasitacianine fluorescence will be deemed a clinically significant event (CSE) • Alteration to initial Completeness of Cytoreduction scores following imaging with pegasitacianine 
Secondary Endpoints:
 
 • Acceptable safety profiles following pegasitacianine administration • Sensitivity • Specificity • NPV • PPV
Study Drug	
m /k of pegasitacianine
 
prior to surgery

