9.3 Rate of Clinically Significant Events

Determining the rate of clinically significant events (CSE) detected by pegasitacianine at the subject-level is the primary objective of this study. CSEs will include pegasitacianine detection of

occult disease not otherwise known by the surgeon to exist, the detection of a positive surgical margin, and accurate identification of tumor negative SOC biopsies. A list of CSEs and their definitions is provided below.

- Detection of Occult Disease or Positive Surgical Margins – identification of tumor-containing tissue due to pgsitacianine fluorescence, confirmed via histopathological analysis, that otherwise went undetected during pre-operative imaging (PET, MRI) or by the surgeon during SOC surgery
 - This occurs when a sample that (1) exhibits fluorescence *in situ* and (2) is pathologically-confirmed as a tumor, is obtained by fluorescence during SOC surgery.
- Tumor Negative SOC Biopsies – during SOC surgery, the surgeon will collect tissue specimens that are suspicious for disease. If those samples do not demonstrate pgsitacianine fluorescence and are found to be devoid of tumor pathologically, those specimens would be included as a tumor negative SOC biopsy
 - This occurs when a sample that (1) exhibits no fluorescence *ex situ* and (2) is pathologically-confirmed as normal tissue, is classified as suspicious tissue during SOC surgery.
- Alteration to the Completeness of Cytoreduction (CC) Score – following the completion of the SOC surgery, the surgeon will document a CC score prior to fluorescence imaging using pgsitacianine. If the surgeon finds residual disease using fluorescence imaging that results in the increase of the CC score, this will be considered a CSE

The number and proportion (with corresponding two-sided exact 95% confidence intervals) of subjects with any CSE will be reported.

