9.4 Imaging Analysis

Diagnostic performance of pgsitacianine will be assessed at the level of the specimen by calculating the *ex situ* sensitivity, specificity, PPV, and NPV of pgsitacianine in detecting tumor containing tissue. The *ex situ* fluorescence status of collected SOC and pgsitacianine guided specimens will be compared to the histological analyses of the collected specimens (which is used to determine each sample's status as true/false positive/negative). For determining these operating characteristics, consider the following definitions:

- False positive is defined as “fluorescence was observed on the specimen but the specimen was not found to have tumor via histological analysis”.
- False negative is defined as “no fluorescence was observed on the specimen but the specimen was found to have tumor via histological analysis”.

- True positive is defined as “fluorescence was observed on the specimen and the specimen was found to have tumor via histological analysis”.
- True negative is defined as “no fluorescence was observed on the specimen and the specimen was found not to have tumor via histological analysis”.

The number of specimens in each category (each combination of true/false positive/negative), along with the true/false positive/negative rates (and corresponding exact two-sided 95% confidence intervals) will be reported. These rates will be used to determine pegsitacianine’s tumor detection sensitivity, specificity, PPV, and NPV using the following equations:

$$\text{Sensitivity} = \frac{\text{\# of True Positive Specimens}}{\text{\# of True Positive + False Negative Specimens}}$$

$$\text{Specificity} = \frac{\text{\# of True Negative Specimens}}{\text{\# of True Negative Specimens + \# of False Positive Specimens}}$$

$$\text{PPV} = \frac{\text{\# of True Positive Specimens}}{\text{\# of True Positive + False Positive Specimens}}$$

$$\text{NPV} = \frac{\text{\# of True Negative Specimens}}{\text{\# of Tumor Negative + False Negative Specimens}}$$

These rates will be reported along with exact two-sided 95% confidence intervals.

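### Neither document masks pathology to fluorescence status or specimen origin, so the reference standard for the accuracy measures and for two of the three CSE types has no guard against review bias

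*Protocol*

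**What the plan says.** Protocol 5.4 is a single line: "Not applicable; this is an open label study". The sections on either side, on randomization and on breaking the blind, are also marked as not applying.

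Histology is the truth for most of what the trial estimates:

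- **Accuracy measures.** Under Protocol 9.4, the ex situ fluorescence of SOC and "guided specimens will be compared to the histological analyses of the collected specimens". Every true or false positive or negative follows from that comparison. SAP 5.1.2 uses the same definitions.
- **Occult disease or positive margin CSE.** Protocol 9.3 requires "identification of tumor-containing tissue due to pgsitacianine fluorescence, confirmed via histopathological analysis".
- **Tumor-negative SOC biopsy CSE.** Protocol 9.3 counts a specimen without ex situ fluorescence that "is pathologically-confirmed as normal tissue, is classified as suspicious tissue during SOC surgery".
- **CC-score CSE.** Here "the surgeon will document a CC score prior to fluorescence imaging using pgsitacianine", and an increase after imaging counts. No pathology condition is stated. SAP 5.1.1 repeats all three types and makes a subject with any one of them a responder.

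Protocol 3.1 says that fluorescence status, "as called out by the surgeon, will then be directly correlated to the histopathological outcomes of each specimen dictated in the final pathology report". On naming, the Protocol Summary says: "Specimen names and fluorescence status will be dictated by the surgeon and documented in the Imaging Workbook by the research coordinator". The Appendix 1 footnote on pathology places the reading after surgery, within 10 days.

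**The concern.** In a diagnostic accuracy study the reader of the reference standard should not know the index test result. Here the index result exists before pathology starts. For specimens taken after SOC resection, origin alone reveals it, because they were removed for fluorescing. Protocol 1.1 says the disease sought may be microscopic, so how much tissue is examined can decide the call.

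A reader who knew the status could shift results in three ways:

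- Over-calling tumour in a guided specimen adds a false occult-disease CSE.
- Searching a non-fluorescent suspicious specimen less thoroughly can turn a false negative into a true negative. The same specimen then becomes a tumor-negative SOC biopsy CSE.
- Unequal search effort between fluorescent and non-fluorescent specimens distorts the accuracy comparison.

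All three favour the agent. The estimates are meant to help power future studies (Protocol 9.1), and the Protocol makes sensitivity and specificity of at least 70% in Group 1 the condition for opening Group 2 (the SAP leaves this to the sponsor). An upward shift would carry into both uses.

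**Working it through.** **Is there a safeguard anywhere?** The plan gives no figure to reproduce, so the first check is of the text.

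- Protocol 5.4 and 5.5: no masking of any party.
- Protocol 3.1, 6.3 and Summary: name and status go from the surgeon to the coordinator. There is no coded label and no statement of what reaches pathology.
- Protocol 6.5: sponsor representatives may not influence specimen selection or fluorescence status. This does not cover pathology.
- Protocol 9.3 and 9.4, SAP 5.1.1 and 5.1.2: histology as truth, with no masked, central or second read and no common sectioning rule.
- SAP 7.10.3: the ROC, clustering and camera analyses take tumour status from the same pathology, so none of them tests it.

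The reverse direction is protected: the surgeon calls fluorescence before pathology, so the histology result cannot influence that call.

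**How large could it be?** Every rate below is an assumption. Only the ceiling of 15 SOC specimens (10 suspected tumour, 5 normal) and the 60 subjects come from the documents.

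*A. Lighter search of non-fluorescent specimens.* Per patient, take 10 tumour and 5 normal specimens, sensitivity 85%, specificity 70%. Then TP = 8.5, FN = 1.5, TN = 3.5, FP = 1.5. Move a share f of FN to TN:

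- Sensitivity = 8.5 / (8.5 + 1.5(1 - f))
- Specificity = (3.5 + 1.5f) / (5 + 1.5f)
- NPV = (3.5 + 1.5f) / 5

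| f | Sensitivity | Specificity | NPV |
|---|---|---|---|
| 0 | 0.850 | 0.700 | 0.70 |
| 10% | 8.5/9.85 = 0.863 | 3.65/5.15 = 0.709 | 0.73 |
| 20% | 8.5/9.70 = 0.876 | 3.80/5.30 = 0.717 | 0.76 |
| 30% | 8.5/9.55 = 0.890 | 3.95/5.45 = 0.725 | 0.79 |

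PPV stays at 8.5/10 = 0.85, because no fluorescent specimen is reclassified.

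*B. Errors in both directions, smaller shares.* Take 60 x 15 = 900 specimens, 480 with tumour (80% of the 600 suspected), sensitivity 80%, specificity 70%. Then TP = 384, FN = 96, TN = 294, FP = 126. Move 2%, 5% or 10% of FP to TP and of FN to TN:

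| Share | Sensitivity | Specificity | PPV | NPV |
|---|---|---|---|---|
| 0 | 80.0% | 70.0% | 75.3% | 75.4% |
| 2% | 80.4% | 70.6% | 75.8% | 75.9% |
| 5% | 81.1% | 71.4% | 76.5% | 76.6% |
| 10% | 82.1% | 72.8% | 77.8% | 77.9% |

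*C. Over-calling guided specimens, patient level.* With true CSE rate p, k tumour-free guided specimens in each patient without a CSE, and each over-called independently with probability f, the reported rate is p + (1 - p)(1 - (1 - f)^k). For k = 1 to 3 and f = 2% to 10%, p = 50% becomes 51.0% to 63.6%, and p = 30% becomes 31.4% to 49.0%. For scale, the exact 95% interval for 30/60 is 36.8% to 63.2%.

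**The case against.** The strongest reply is that silence is not exposure. The dictated name and status go to the coordinator for the Imaging Workbook. No section sends either to pathology or makes the dictated name the requisition label, and masking may be set out in a manual that is not provided. The position of 5.4 suggests that it addresses treatment blinding and does not rule on the reference standard. This stands: a reader might infer that the pathologist is told which specimens fluoresced, and the documents do not show that. What remains is that nothing prevents it.

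Three other inferences go too far:

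- **Every CSE depends on pathology.** It does not. The CC-score CSE rests on the surgeon's scores, and the Protocol Summary also lists CC-score change as a primary endpoint in its own right.
- **Closer sectioning of guided specimens creates false primary events.** Tumour found that way is real residual disease, which the primary objective sets out to detect. Unequal search distorts the accuracy measures. A false occult-disease event needs tumour-free tissue to be over-called.
- **The damage could never be checked.** If slides are kept, a masked re-read could test for over-calling. It could not recover tissue that was never sectioned.

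It is also fair to say that this is a pilot not powered for hypothesis testing, that the inputs above are assumed, and that the effect may be small where histology is clear-cut. Calculation A in particular treats all 10 suspected specimens as containing tumour and omits guided specimens. These points limit the size claimed. They give no reason to leave the reader unmasked when masking costs so little.

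**Conclusion.** The point holds as an unguarded risk of review bias. The trial's open-label status does not justify leaving the reference standard unmasked, and the gap touches all four accuracy measures and two of the three CSE types. If the reader knew the status and leaned toward agreeing with it, the shift would favour the agent.

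The documents do not allow the size to be derived. Under the assumptions of calculation A, sensitivity rises by about 1 to 4 points, specificity by about 1 to 3 and NPV by 3 to 9. Under the smaller shares in B, sensitivity and specificity each move by less than 3 points. The effect on the CSE rate depends wholly on the over-calling probability and the number of tumour-free guided specimens, neither of which the plan gives. The confidence intervals would not reveal the shift, because they describe sampling error only. This is a worthwhile low-cost improvement; it does not show that the results are biased.

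**What to change.** Amend Protocol 5.4 and 6.3 to say that the drug is open label but that pathology is masked to fluorescence status, to SOC or guided origin, and to the suspicious or normal designation, until the final pathology report is issued. Specifically:

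- Send study specimens under random, non-sequential codes. Guided specimens are all taken after SOC resection, so running numbers would place them last and reveal their origin.
- Give the anatomical site and any margin or orientation information that the routine report needs. Site alone would not be enough, because a positive margin is itself a CSE.
- Apply the same sectioning approach to all study specimens.
- Keep the code key in the Imaging Workbook and record any unmasking.

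If masking is already set out in a manual, 5.4 should refer to it.

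The cost is a code key for the coordinator, changed requisition wording and brief site retraining. No extra reader is needed, and sample size and endpoints are unchanged. Masking may be incomplete for some specimens, which is why unmasking should be recorded.
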